Appendix 9.	Protocol Amendment I8F-MC-GPHG(d) Summary: A Randomized, Placebo-Controlled, Crossover Study to Investigate the Effect of Once-Weekly Tirzepatide on the Counter- Regulatory Response to Hypoglycemia in Patients with Type 2 Diabetes Mellitus.....	96

1. Protocol Synopsis

Title of Study:

A Randomized, Placebo-Controlled, Crossover Study to Investigate the Effect of Once-Weekly Tirzepatide on the Counter-Regulatory Response to Hypoglycemia in Patients with Type 2 Diabetes Mellitus.

Rationale:

Study I8F-MC-GPHG (Study GPHG) is an approximately 38 to 42 week Phase 1 study designed to examine the effect of tirzepatide (LY3298176) on hypoglycemic counter-regulation in patients with type 2 diabetes mellitus (T2DM) when compared to placebo treatment. Tirzepatide is a long-acting, dual incretin mimetic (dual agonist) that binds to the glucose-dependent insulinotropic polypeptide receptor (GIPR) and the glucagon-like peptide-1 (GLP-1) receptor (GLP-1R). Dual GIPR and GLP-1R agonism may provide improved glycemic control in patients with T2DM, engaging multiple physiologic pathways, including glucagon secretion by the pancreatic α cell. Since glucagon plays a key role in defense against hypoglycemia, it is important to assess the effects of tirzepatide on the physiologic response to hypoglycemia. Understanding the effect of tirzepatide on the counter-regulatory response to a hypoglycemic stimulus will provide important safety information for potential future clinical use.

Objectives/Endpoints:

Objectives	Endpoints

Primary
 
To compare the effect of tirzepatide 15 mg once-weekly (QW) and placebo on glucagon response during hypoglycemia in T2DM patients following 12 weeks of treatment
	
Change in mean glucagon concentration during induced hypoglycemia from target plasma glucose (PG) concentration of 100 mg/dL to a nadir target of 45 mg/dL


Secondary
 
To compare the effect of tirzepatide 15 mg QW and placebo in T2DM patients following 12 weeks of treatment on:
 
 • Other counter-regulatory hormone responses during hypoglycemia, insulin and C-peptide 	
 • Change in mean glucagon concentration from target PG concentration of 100 mg/dL to 63 mg/dL and to recovery (PG concentration 72 mg/dL) from induced hypoglycemia • Change in mean glucagon concentration from ambient PG to target PG concentrations of 100, 63, and 45 mg/dL, and to recovery (PG concentration 72 mg/dL) from induced hypoglycemia • Change in mean insulin, C-peptide, growth hormone, cortisol, adrenaline, and noradrenaline concentrations from target PG concentration of 100 mg/dL to 63 and 45 mg/dL, and to recovery (PG concentration 72 mg/dL) from induced hypoglycemia

 • Time to hypoglycemia recovery 	
 • Time from termination of insulin infusion at PG concentration of 45 mg/dL to reach recovery PG concentration (72 mg/dL) (tPG_nadir-72 mg/dL)

 Clinical hypoglycemia 	
 Hypoglycemic symptoms score at PG concentrations of 100, 63, and 45 mg/dL and after recovery (PG concentration 72 mg/dL) from induced hypoglycemia Hypoglycemic awareness at PG concentrations of 100, 63, and 45 mg/dL and after recovery (PG concentration 72 mg/dL) from induced hypoglycemia

 Vital signs during hypoglycemia 	
 Change in mean systolic and diastolic blood pressure and pulse rate from target PG concentration of 100 mg/dL to 63, and 45 mg/dL, and to recovery (PG concentration 72 mg/dL) from induced hypoglycemia

 Additional safety and tolerability 	
 Adverse events (AEs) Incidence of hypoglycemia outside of the hypoglycemic clamps

Plasma glucose concentrations: 100 mg/dL = 5.5 mmol/L; 72 mg/dL = 4.0 mmol/L; 63 mg/dL = 3.5 mmol/L; 45 mg/dL = 2.5 mmol/L; glucagon at ambient PG measured in the pre-prandial state prior to clamp initiation.

Summary of Study Design:

This is a Phase 1, single-center, 2-period, crossover, randomized, patient- and investigator-blind study in T2DM patients. This study is designed to compare tirzepatide 15 mg QW and placebo with respect to secretion of counter-regulatory hormones in response to a hypoglycemic stimulus and parameters of recovery from hypoglycemia.

Eligibility for this study for patients on metformin only will be assessed at the screening (Visit 1) up to 17 days prior to enrollment (Day -14 ± 3) and confirmed at the beginning of the lead-in period (Visit 2).

Eligibility for patients on metformin and one other oral antidiabetic medication (OAM) will be assessed at the screening (Visit 1) up to 45 days prior to enrollment and confirmed at the beginning of the lead-in period (Visit 2), followed by discontinuation and a washout period for OAMs, other than metformin. The washout period for these patients will last at least 4 weeks between Visit 2 and Visit 3.

Eligible patients will undergo 2 treatment periods and will be randomized (Visit 3) to receive tirzepatide 15 mg QW in 1 period followed by placebo in the other, or vice versa, in a crossover fashion. Tirzepatide 15 mg will be attained via step-wise dose escalation to reduce the risk of gastrointestinal AEs.

There will also be a washout period of at least 8 weeks between the last dose of study drug in Period 1 and the first dose in Period 2.

At the end of each treatment period, patients will undergo a hypoglycemic clamp procedure.

Treatment Arms and Planned Duration for an Individual patient:

Each patient will receive tirzepatide 15 mg followed by placebo or vice versa in a crossover fashion. Tirzepatide dosing will start at a dose of 2.5 mg QW for 2 weeks, followed by step-wise escalation to 5 mg QW for the next 2 weeks, 10 mg QW for the next 4 weeks, and 15 mg QW for the final 4 weeks.

The planned study duration for an individual patient from screening through safety follow-up will be approximately 38 to 42 weeks.

Number of Patients:

Approximately 38 patients are planned to be enrolled so that 30 patients complete the study.

Statistical Analysis:

The primary pharmacodynamic (PD) parameter for analysis will be the change in mean glucagon concentration between the 100 mg/dL (5.5 mmol/L) clamp step and the nadir target 45 mg/dL (2.5 mmol/L) step. This will be evaluated using a linear mixed-effects model, with treatment, treatment period, and treatment sequence as fixed effects, and patient as a random effect. From the model, the difference between tirzepatide and placebo in least squares means estimates and the corresponding 95% confidence intervals for the difference will be calculated.

The secondary PD measures for statistical analysis are:

- Change in mean glucagon concentration from target PG concentration of 100 mg/dL (5.5 mmol/L) to 63 mg/dL (3.5 mmol/L) and to recovery (PG concentration 72 mg/dL [4.0 mmol/L]) from induced hypoglycemia
- Change in mean glucagon concentration from ambient PG to target PG concentrations of 100, 63, and 45 mg/dL (5.5, 3.5, and 2.5 mmol/L), and to recovery (PG concentration 72 mg/dL [4.0 mmol/L]) from induced hypoglycemia
- Change in mean insulin, C-peptide, growth hormone, cortisol, adrenaline, and noradrenaline concentrations from target PG concentration of 100 mg/dL (5.5 mmol/L), to 63 and 45 mg/dL (3.5 and 2.5 mmol/L), and to recovery (PG concentration 72 mg/dL [4.0 mmol/L]) from induced hypoglycemia
- $t_{PG_nadir-72\ mg/dL}$

These parameters will be analyzed using a similar model to that described for the primary endpoint. If the $t_{PG_nadir-72\ mg/dL}$ is highly skewed, a log-transformation may be considered. If the assumptions of the model appear to be violated, a non-parametric analysis may be performed.

Change in mean systolic and diastolic blood pressure and pulse rate from target PG concentration of 100 mg/dL (5.5 mmol/L) to 63, 45, and 72 mg/dL (3.5, 2.5, and 4.0 mmol/L), and hypoglycemic symptom and awareness scores at target PG concentrations of 100, 63, and 45 mg/dL (5.5, 3.5, 2.5 mmol/L) and after recovery (PG concentration 72 mg/dL [4.0 mmol/L]) from induced hypoglycemia will be listed and summarized.

2. Schedule of Activities

Study Schedule Protocol I8F-MC-GPHG: Screening, Lead-in, Randomization/Dose 1 Period 1, and Dose 1 Period 2

Procedure	Screening	Lead-in (with or without washout)	Randomization and Dose 1, Treatment Period 1	Dose 1, Treatment Period 2	Comments
Visit	1	2	3	10	
Study Period Week	-6/-2 ^a	-5/-1 ^a	1	1	
Study Period Day	-14 ±3 ^a or -42 ±3 ^a	-7 ± 3 ^a or -35 ±3 ^a (prior to randomization)	1	1	Patients on metformin only should perform Visits 1 and 2 approximately 2 and 1 week prior to Visit 3. Patients on metformin and one additional OAM should perform Visit 1 about 6 weeks prior to Visit 3, in order to permit eligibility assessment at Visit 2. OAMs other than metformin will be discontinued immediately after Visit 2 followed by at least 4-weeks washout between Visit 2 and Visit 3.
Informed consent	X				
Medical history	X				
Drug and alcohol screen	X				May be repeated throughout the study as deemed necessary by the investigator.
Physical examination / medical assessments	X				Full physical examination at screening. After screening, medical assessments only performed to include medical review and targeted examination, as appropriate.
Height	X				
Weight	X		P	P	
Vital signs (BP/PR/body temperature)	X		P	P	Blood pressure and PR measurements will be taken after at least 5 minutes in the supine position.
ECGs	X		P	P	Single 12-lead ECGs will be collected. Electrocardiograms will be recorded using equipment available at the CRU. Patients must be supine for at least 5 minutes before ECG collection, and remain supine but awake during ECG collection.
AEs			X		

Procedure	Screening	Lead-in (with or without washout)	Randomization and Dose 1, Treatment Period 1	Dose 1, Treatment Period 2	Comments
Visit	1	2	3	10	
Study Period Week	-6/-2 ^a	-5/-1 ^a	1	1	
Study Period Day	-14 ±3 ^a or -42 ±3 ^a	-7 ±3 ^a or -35 ±3 ^a (prior to randomization)	1	1	Patients on metformin only should perform Visits 1 and 2 approximately 2 and 1 week prior to Visit 3. Patients on metformin and one additional OAM should perform Visit 1 about 6 weeks prior to Visit 3, in order to permit eligibility assessment at Visit 2. OAMs other than metformin will be discontinued immediately after Visit 2 followed by at least 4-weeks washout between Visit 2 and Visit 3.
Concomitant medications	X		X		
Inclusion/exclusion criteria	X	X			For patients requiring OAM washout, eligibility must be confirmed prior to discontinuing the OAM.
Randomization			P		To occur after all other predose assessments are conducted.
Investigational Product					
Tirzepatide or placebo administration			X	X	
Clinical Procedures					
Outpatient visit	X	X	X	X	
Laboratory Tests					
Safety laboratory tests	X		P	P	See Appendix 2 for details. Patients will fast for at least 8 hours before each blood sample is collected (fasting). If not fasted prior to screening, patient may return for test within the screening window.
Serology	X				See Appendix 2 for details.
Pregnancy test (women of childbearing potential)	X	X ^b	P	P	Serum pregnancy test will be performed at screening. Urine pregnancy test will be performed at other times. Performed by local laboratory or on site.
Insulin, C-peptide			P	P	Fasting. Performed by central laboratory.

Procedure	Screening	Lead-in (with or without washout)	Randomization and Dose 1, Treatment Period 1	Dose 1, Treatment Period 2	Comments
Visit	1	2	3	10	
Study Period Week	-6/-2 ^a	-5/-1 ^a	1	1	
Study Period Day	-14 ±3 ^a or -42 ±3 ^a	-7 ±3 ^a or -35 ±3 ^a (prior to randomization)	1	1	Patients on metformin only should perform Visits 1 and 2 approximately 2 and 1 week prior to Visit 3. Patients on metformin and one additional OAM should perform Visit 1 about 6 weeks prior to Visit 3, in order to permit eligibility assessment at Visit 2. OAMs other than metformin will be discontinued immediately after Visit 2 followed by at least 4-weeks washout between Visit 2 and Visit 3.
Glucagon			P	P	Fasting. Performed by central laboratory.
Calcitonin	X				Fasting. If not fasted prior to screening, patient may return for test within the screening window. Central laboratory.
Glucose Management					
Dispense blood glucose meters, test strips, study diaries, and disease management training		X			These SMPG-related procedures will be performed after eligibility is confirmed.
SMPG		X		X	For patients undergoing OAM washout, phone interviews will be conducted during lead-in to assess acceptability of glycemic control. Refer to Section 5.1.1 for further details
Review of study diary for SMPG			P	P	

Procedure	Screening	Lead-in (with or without washout)	Randomization and Dose 1, Treatment Period 1	Dose 1, Treatment Period 2	Comments
Visit	1	2	3	10	
Study Period Week	-6/-2 ^a	-5/-1 ^a	1	1	
Study Period Day	-14 ±3 ^a or -42 ±3 ^a	-7 ±3 ^a or -35 ±3 ^a (prior to randomization)	1	1	Patients on metformin only should perform Visits 1 and 2 approximately 2 and 1 week prior to Visit 3. Patients on metformin and one additional OAM should perform Visit 1 about 6 weeks prior to Visit 3, in order to permit eligibility assessment at Visit 2. OAMs other than metformin will be discontinued immediately after Visit 2 followed by at least 4-weeks washout between Visit 2 and Visit 3.
Diagnostics					
PK sample			P	P	PK and immunogenicity to be time-matched as much as possible.
Immunogenicity			P	P	
Pharmacogenetic sample			P		Single sample taken predose on Day 1 Period 1.
Nonpharmacogenetic stored samples			P	P	Fasting sample.

Abbreviations: AE = adverse event; BP = blood pressure; ECG = electrocardiogram; FSH = follicle-stimulating hormone; P = predose; PK = pharmacokinetic; PR = pulse rate; SMPG = self-monitoring of blood glucose.

a Visit windows are relative to randomization (Period 1, Day 1).

b A serum pregnancy test will be taken during Visit 2 if the FSH ≤40mIU/mL at Visit 1.

Note: If multiple procedures take place at the same time point, the following order may be consulted for prioritization: ECG, vital signs, counter-regulatory hormone samples, safety laboratory tests, PK samples, immunogenicity samples, storage samples.

Study Schedule Protocol I8F-MC-GPHG: Treatment Periods 1 and 2

Procedure	Treatment Periods 1 and 2												Comments		
Visit Period 1	4	5		6			7			8	9	9			
Visit Period 2	11	12		13			14			15	16	16			
Study Period Week	2	3	4	5	6	7	8	9	10	11	12	12			
Study Period Day	8 ±1	15 ±1	22	29 ±1	36	43	50	57 ±1	64	71	78 ±2	79 ±2	80 ±2	Patients should attend on stated day. When the patient is unable to attend CRU on the stated day, visit windows should be used for dosing only. Days 78, 79, and 80 should occur consecutively, without interruption.	
Weight				P			P			P					
Vital signs (BP/PR/body temperature)	P	P		P			P			P	X See Appendix 6		Refer to screening table.		
ECGs				P						P	X See Appendix 6		Refer to screening table.		
Concomitant medications	X														
AEs	X														
Physical examination / medical assessments	X									X			Refer to screening table.		
Alcohol breath test											X				
CRU admission											X				
CRU discharge												X			
Outpatient visit	X	X		X			X			X					
Dispense study treatment		X		X			X						For outpatient use.		
Telephone visit			X		X			X					May be more frequent if there is evidence of missed doses.		
Investigational Product															
Tirzepatide or placebo administration	X	X	X	X	X	X	X	X	X	X			Patients will self-administer study drug when not in CRU.		

Procedure	Treatment Periods 1 and 2												Comments	
Visit Period 1	4	5		6			7			8	9	9		
Visit Period 2	11	12		13			14			15	16	16		
Study Period Week	2	3	4	5	6	7	8	9	10	11	12	12		
Study Period Day	8 ±1	15 ±1	22	29 ±1	36	43	50	57 ±1	64	71	78 ±2	79 ±2	80 ±2	Patients should attend on stated day. When the patient is unable to attend CRU on the stated day, visit windows should be used for dosing only. Days 78, 79, and 80 should occur consecutively, without interruption.
Glucose Management														
SMPG	X													
Fasting blood glucose	P	P											The central laboratory will test fasting blood glucose.	
Review of study diary for SMPG	X	X		X				X			X			
Laboratory Tests														
Safety laboratory tests				X						X			Refer to screening table.	
Pregnancy test (women of childbearing potential)				X				X			X		Refer to screening table.	
Insulin, C-peptide												X See Appendix 6	Fasting. Performed by central laboratory.	
Growth hormone, cortisol													Fasting. Performed by central laboratory.	
Adrenaline, noradrenaline													Fasting. Performed by central laboratory.	
Glucagon													Fasting. Performed by central laboratory.	

Procedure	Treatment Periods 1 and 2												Comments	
Visit Period 1	4 11	5 12		6 13			7 14			8 15	9 16	9 16		
Visit Period 2														
Study Period Week	2	3	4	5	6	7	8	9	10	11	12	12		
Study Period Day	8 ±1	15 ±1	22	29 ±1	36	43	50	57 ±1	64	71	78 ±2	79 ±2	80 ±2	Patients should attend on stated day. When the patient is unable to attend CRU on the stated day, visit windows should be used for dosing only. Days 78, 79, and 80 should occur consecutively, without interruption.
Investigative Tests														
Hypoglycemic clamp													X See Appendix 6	
Diagnostics														
PK sample				P						P			PK and immunogenicity to be time-matched as much as possible.	
Immunogenicity				P						P				
Nonpharmacogenetic stored samples										P			Fasting sample.	
Cognitive Assessments														
Hypoglycemic symptom awareness													X See Appendix 6	
Hypoglycemic symptoms score														

Abbreviations: AEs = adverse events; BP = blood pressure; CRU = clinical research unit; ECG = electrocardiogram; P = predose; PK = pharmacokinetics; PR = pulse rate; SMPG = self-monitoring of plasma glucose.

Note: If multiple procedures take place at the same time point, the following order may be consulted for prioritization: ECG, vital signs, glucose sampling, counter-regulatory hormone samples, safety laboratory tests, PK samples, immunogenicity samples, cognitive assessments, storage samples.

Study Schedule Protocol I8F-MC-GPHG: Washout Period

Procedure	Washout Period
Visit	
Study Week ^a	12-20 (12-22)
Study Day ^a	81-135 (81-149)
Clinical Procedures	
Washout / crossover	X
Concomitant medications	X ^b
AEs	X ^b
Glucose Management	
SMPG	X ^b

Abbreviations: AEs = adverse events; SMPG = self-monitoring of plasma glucose.

a Washout period is at least 8 weeks and up to 10 weeks, if necessary.

b Data will be reviewed and recorded in the electronic case report form at the dose 1 Period 2 visit.

Study Schedule Protocol I8F-MC-GPHG: Follow-up / Early Termination

Procedure	ET	Final FU	Comments
Visit	-	17	
Study Week	-	36	
Study Day	As soon as possible after discontinuation decision	Within 4 weeks from last dose/ET	
Clinical Procedures			
Weight	X	X	
Vital signs (BP/PR/body temperature)	X	X	Refer to screening table.
ECGs	X	X	Refer to screening table.
Concomitant medications	X	X	
AEs	X	X	
Physical examination / medical assessments	X	X	Refer to screening table.
Outpatient visit	X	X	
Glucose Management			
Review of study diary for SMPGa	X	X	
Study diary collection		X	
Laboratory Tests			
Pregnancy test (women of childbearing potential)	X	X	Refer to screening table.
Diagnostics			
PK sample	X	X	Samples for immunogenicity and PK to be time-matched as far as possible.
Immunogenicity	X	X	

Abbreviations: AEs = adverse events; BP = blood pressure; ECG = electrocardiogram; ET = early termination; FU = follow-up; PK = pharmacokinetics; PR = pulse rate; SMPG = self-monitoring of plasma glucose;

a SMPG will continue until Follow-up visit.

Note: If multiple procedures take place at the same time point, the following order may be consulted for prioritization: ECG, vital signs, PK samples, immunogenicity samples.

3. Introduction

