5.1.2. Treatment

The tirzepatide treatment period will consist of a step-wise dose escalation. The starting dose will be 2.5 mg QW for 2 weeks, followed by an increase to 5 mg QW for 2 weeks, and 10 mg QW for 4 weeks until the 15-mg dose is reached and maintained for the remainder of the treatment period (4 weeks), see Section 5.5 (Justification for Dose) for further details. Patients will visit the clinical research unit (CRU) as outpatients 1 week after administration of the first dose (Week 2) and for administration of the first of each escalated dose during both the tirzepatide and placebo treatment periods (Weeks 3, 5 and 9 of each treatment period). Study drug will be dispensed to the patient at these visits for self-administration on all other dosing days. Telephone visits will be conducted to ensure that outpatient dosing occurs and to monitor safety.

The schedule of clinic visits and study procedures during the treatment periods, including sampling for immunogenicity and pharmacokinetic (PK) assessments, are provided in Section 2 (Schedule of Activities).

Patients will attend the CRU as outpatients on Week 12 of each treatment period to receive the final dose of study drug. The following day, patients will be admitted to the CRU and will undergo a hypoglycemic clamp procedure as detailed in Appendix 6.

Patients who initiate rescue medication for treatment of severe hyperglycemia (Section 7.4.1.2 Management of Hyperglycemia) during the study may continue in the study but rescue medication will be discontinued 1 week before the clamp procedure to avoid interference with measurements planned during the hypoglycemic clamp.

Patients who permanently discontinue study treatment early, irrespective of the reason, will be discontinued from the study (Section 8.1 Discontinuation from Study Treatment). They will perform an early termination (ET) visit as soon as possible after the decision to discontinue study treatment, followed by a safety follow-up visit up to 4 weeks later.

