8.1. Discontinuation from Study Treatment

8.1.1. Permanent Discontinuation from Study Treatment

Possible reasons leading to permanent discontinuation of IP:

- The patient requests to discontinue IP
- If a patient is inadvertently enrolled and it is determined that continued treatment with study drug would not be medically appropriate (Section 8.1.3 Discontinuation of Inadvertently Enrolled Patients)
- If a patient is diagnosed with acute or chronic pancreatitis after randomization
- If a patient is diagnosed with MTC after randomization
- If a patient is diagnosed with an active or untreated malignancy (other than basal or squamous cell skin cancer, in situ carcinomas of the cervix, or in situ prostate cancer) after randomization
- If a patient is diagnosed with a significant study drug-related hypersensitivity reaction
- If a patient is diagnosed at any time, including during the hypoglycemic clamp procedure, with any other TEAE, SAE, or clinically significant laboratory value for which the investigator believes that permanent study drug discontinuation is the appropriate measure to be taken
- If a female patient becomes pregnant
- If a patient is diagnosed with type 1 diabetes mellitus
- Drug-related vomiting requiring IV hydration treatment or causing severe distress (prevents daily activities and results in no appetite, or requires an emergency department visit or hospitalization), that cannot be resolved by temporary interruption of study drug (Section 8.1.2 Temporary Interruption of Study Drug)

Discontinuation of the IP for abnormal liver function tests **should be considered** by the investigator when a patient meets any of the following conditions after consultation with the Lilly-designated medical monitor:

- ALT or AST >8X ULN
- ALT or AST >5X ULN sustained for more than 2 weeks or
- ALT or AST >3X ULN and TBL >2X ULN or international normalized ratio >1.5 or

- ALT or AST >3X ULN with the appearance of fatigue, nausea, vomiting, right upper-quadrant pain or tenderness, fever, rash, and/or eosinophilia (>5%)
- alkaline phosphatase (ALP) >3X ULN
- ALP >2.5X ULN and TBL >2X ULN
- ALP >2.5X ULN with the appearance of fatigue, nausea, vomiting, right quadrant pain or tenderness, fever, rash, and/or eosinophilia (>5%)

Patients who discontinue study drug early will also be discontinued from the study after performing ET visit and safety follow-up visit procedures, as specified in Section 2 (Schedule of Activities).

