Appendix 5. Blood Sampling Summary

This table summarizes the approximate number of venipunctures and blood volumes for all blood sampling (screening, safety laboratories, and bioanalytical assays) during the study.

Protocol I8F-MC-GPHG Sampling Summary

Purpose	Blood Volume per Sample (mL)	Number of Blood Samples	Total Volume (mL)
Screening tests ^a	23	1	23
Safety laboratory tests ^a	15	6	90
Pharmacokinetics	3	8	24
Fasting blood glucose	2	4	8
Plasma glucose sampling (clamp)	20 (per clamp)	2	40
Fasting insulin, C-peptide	2.5	22	55
Glucagon	2	24	48
Growth hormone, cortisol	4	20	80
Adrenaline, noradrenaline	5	20	100
Immunogenicity	10	8	80
Pharmacogenetics	10	1	10
Nonpharmacogenetics	9	4	36
Total			594
Total for clinical purposes			600

^a Additional samples may be drawn if needed for safety purposes.

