6.10. Safety Analyses

Safety measures include, but not limited to, AEs, treatment-emergent adverse events (TEAEs), serious adverse events (SAEs), adverse events of special interest (AESIs), vital signs, and safety laboratory measures.

Unless specified otherwise, safety analyses will be performed on the safety population.

Unless specified otherwise, safety listings will display values/events during all study periods (i.e., treatment periods, washout, and follow-up period). Listings of AEs, death, SAE may include (but not limited to): patient identification (ID) number, age, sex, race, treatment, dose, Medical Dictionary for Regulatory Activities (MedDRA) System Organ Class (SOC), Preferred Term (PT), and time of onset from the first dose of study drug, duration of the AE, seriousness, severity, relatedness to study drug, action taken, and outcome, as appropriate. Additional safety listings will be provided for safety parameters other than AEs in related sections below. Treatment, and treatment period will be displayed in listings.

For safety measurements, summary statistics will be provided by treatment. A summary will be provided for AEs with frequency ≥ 10 patients with such event.

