6.10.6. Vital Signs

Descriptive summaries of vital signs will be provided for actual values of Day 1, Day 8, Day 15, Day 29, Day 57, Day 78 by treatment for each period, and by treatment only, and change from Day 1 values by treatment for each period, and by treatment only. Plots of mean vital signs and mean changes from Day 1 over time will be provided by treatment for each period.

The treatment-emergent abnormal vital signs will be listed. The criteria for identifying patients with treatment-emergent vital sign abnormalities are stated in [Table GPHG.8](#).

Table GPHG.8. Categorical Criteria for Treatment-Emergent Abnormal Blood Pressure and Pulse Measurements

Parameter	Low	High
Systolic BP (mmHg) (Supine or sitting – forearm at heart level)	≤90 and decrease from baseline ≥20	≥140 and increase from baseline ≥20
Diastolic BP (mmHg) (Supine or sitting – forearm at heart level)	≤50 and decrease from baseline ≥10	≥90 and increase from baseline ≥10
Pulse (bpm) (Supine or sitting)	<50 and decrease from baseline ≥15	>100 and increase from baseline ≥15

Abbreviations: BP = blood pressure; bpm = beats per minute.

For PD parameters of systolic, diastolic blood pressure, and pulse rate during hypoglycemic clamp procedures, see Section 6.9 for analyses details.

6.10.7. *Electrocardiogram*

Electrocardiograms will be performed for safety monitoring purposes only. Any clinically significant ECG findings entered as AEs will be included in AE summaries.

6.10.8. *Safety Laboratory Parameters*

All laboratory data will be reported in the International System of Units and conventional units.

Descriptive summaries of clinical chemistry, hematology, and endocrine (calcitonin) data will be provided for actual values of Day 1 predose, Day 29, Day 78, and their changes from Day 1 will by treatment for each period, and by treatment only.

Additionally, clinical chemistry, hematology, urinalysis, and endocrine (calcitonin) data outside the reference ranges will be listed.

If any safety lab measurements are (1) below the quantification limit (e.g. < QL), $\frac{1}{2} \times QL$ may be used for the calculation of summary statistics; (2) above the quantification limit (e.g. > QL), $1.1 \times QL$ may be used for the calculation of summary statistics, if deemed appropriate.

6.11. *Evaluation of Immunogenicity*

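### The early-termination visit schedules no safety laboratory panel, so a patient who stops tirzepatide before Day 78 with no symptom or event to prompt a sample has at most the Day 29 result

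*Protocol*

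**What the plan says.** **Early termination (ET) and follow-up.** The Follow-up / Early Termination table in Protocol Section 2 schedules weight, vital signs, ECG, medication and adverse-event review, medical assessment, diary review, a pregnancy test, and PK and immunogenicity samples. It has no row for safety laboratory tests at either visit. Its note on sampling order reads "the following order may be consulted for prioritization: ECG, vital signs, PK samples, immunogenicity samples". The corresponding notes under the other two visit tables both name safety laboratory tests.

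**Sampling budget.** Appendix 5 sets out to count "blood volumes for all blood sampling (screening, safety laboratories, and bioanalytical assays) during the study". It lists 6 safety-lab samples of 15 mL, 8 PK samples and 8 immunogenicity samples. A footnote leaves room for unscheduled draws: "Additional samples may be drawn if needed for safety purposes".

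**Analysis.** SAP 6.10.8 says that laboratory "data will be provided for actual values of Day 1 predose, Day 29, Day 78", with changes from Day 1, and that out-of-range values will be listed. SAP 6.10 adds that "safety listings will display values/events during all study periods".

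**Exit route.** Under Protocol 5.1.2, patients who stop study drug for any reason leave the study: "They will perform an early termination (ET) visit as soon as possible after the decision to discontinue study treatment", with safety follow-up up to 4 weeks later. Section 8.1.1 agrees: "Patients who discontinue study drug early will also be discontinued from the study after performing ET visit and safety follow-up visit procedures". Its first listed reason for stopping needs no adverse event: "The patient requests to discontinue IP".

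**The concern.** The ET visit is the last routine opportunity to see what the drug has done to laboratory values in a patient who is leaving. As scheduled, blood is drawn there for PK and antibodies, but not for creatinine, liver enzymes, lipase, amylase or hematology.

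Some of the protocol's own monitoring depends on having such a value. Hepatic monitoring (9.4.5.1) starts from an elevated ALT, ALP or bilirubin; an elevation without symptoms cannot start it if no sample is taken. Renal safety (9.2.2.12) rests partly on laboratory renal function. The argument is weaker for pancreatic enzymes, because 9.2.2.4 itself says that serial values predict little in patients without symptoms, but they belong to the same panel.

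At stake is routine safety information in patients who stop for reasons that prompt no test. Besides patient request, the protocol gives two such routes: more than 14 days of weight-loss medication (7.7) and, after review, repeated noncompliance (7.6).

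**Working it through.** **1. Is the missing row real?** Reproduce the Appendix 5 counts from the schedule.
- Safety labs: 2 periods × 3 days (1, 29, 78) = 6. Appendix 5 states 6, at 6 × 15 = 90 mL.
- PK and immunogenicity: 2 × 3 + ET + follow-up = 8 each. Appendix 5 states 8 each.
- All rows: 23 + 90 + 24 + 8 + 40 + 55 + 48 + 80 + 100 + 80 + 10 + 36 = 594 mL, as stated.

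Appendix 5 therefore budgets ET and follow-up draws for PK and antibodies and none for safety labs. The visit table, its sampling-order note, Appendix 5 and the SAP time points all agree, so this is not a table damaged in text extraction.

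**2. What does a tirzepatide stopper have?** Post-dose safety labs scheduled in the tirzepatide period:

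| Stops tirzepatide | Scheduled safety labs after a tirzepatide dose |
|---|---|
| Before Day 29 | 0 of 2 (only fasting glucose on Days 8 and 15) |
| After the Day 29 visit, before Day 78 | 1 of 2 (Day 29) |
| From Day 78 | 2 of 2 |

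A patient who stops in Period 1 never reaches the Period 2 Day 1 lab.

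**3. How much dosing can follow the last scheduled lab?** The doses are 2.5 mg × 2, 5 mg × 2, 10 mg × 4 and 15 mg × 4.
- Full course: 5 + 10 + 40 + 60 = 115 mg.
- The Day 29 lab is marked X rather than predose, so it may come before or after that day's first 10-mg dose. It follows 15 mg (15/115 = 13%) or 25 mg (25/115 = 22%).
- A patient who takes every dose and stops just before Day 78 has had 5 + 10 + 40 + 45 = 100 mg. That is 85 mg or 75 mg beyond the last scheduled lab, with the final dose on Day 71, 42 days after Day 29.

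This is the extreme case. Earlier stops or missed doses reduce it.

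**4. How many patients?** Protocol 10.1 plans 38 enrolled and 30 completing: 38 − 30 = 8, and 8/38 = 21%. Under that assumption, 8 is a ceiling on all ET visits. It includes patients who stop on placebo, after Day 78, or because of an adverse event. The documents give no split by treatment, timing or reason, so the number who stop tirzepatide before Day 78 with no trigger can only be placed between 0 and 8.

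**5. What would an ET panel do to blood volume?**
- Table total: 594 + 15 = 609 mL, against a stated rounded total of 600 mL.
- A completer has no ET draw: 594 − 3 (PK) − 10 (immunogenicity) = 581 mL.
- A patient who stops in Period 2 between Day 29 and Day 78 misses the second clamp (glucose 20 + insulin and C-peptide 25 + glucagon 22 + growth hormone and cortisol 40 + catecholamines 50 = 157 mL). The Day 78 draws are missed too (15 + 3 + 10 + 9 = 37 mL). With an ET panel the total is 609 − 157 − 37 = 415 mL.

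The 609 mL is a sum over table rows; neither of these patients reaches it.

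**The case against.** The strongest reply is that this is a deliberate and consistent design. Schedule, sampling budget and SAP give the same six labs, and nothing in the protocol promises one at ET. That is correct: there is no contradiction to resolve. But consistency does not supply the missing value.

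The second reply is that the patients who matter are already covered. Adverse events that lead to stopping must be followed until resolved, stable or explained (9.2). Extra safety samples are allowed (Appendix 5), and lipase and amylase may be drawn for symptoms (Appendix 7). ET itself includes event review, medical assessment, vital signs and ECG. The documents name gastrointestinal intolerance as the main tolerability problem, so many stoppers may well have a trigger, and a patient's own request may also reflect an adverse event. Section 3.3 reports no other clinically relevant safety concern up to 15 mg. All of this stands. It narrows the gap to stoppers with no trigger and gives no reason to expect a high yield. It does not close the gap, because a discretionary sample needs a reason to be taken.

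A reader might infer more than the documents support:
- *That early stoppers are unmonitored.* They are not, for the reasons above.
- *That eight patients would be affected.* Eight is the planned number of dropouts of every kind. A patient who drops out during placebo in Period 1 also lacks a Day 78 tirzepatide lab, yet was never exposed.
- *That hepatic monitoring has no liver value to work from.* Only those who stop before Day 29 lack a post-dose value; later stoppers have the Day 29 result.
- *That the SAP needs an ET summary time point.* A mean over at most about 8 patients, split by treatment and stopped at anything from 2.5 to 15 mg, would say little. A listing is enough.

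**Conclusion.** The point holds as a limited gap in safety monitoring. Routine safety labs are absent at ET, so a patient who stops tirzepatide before Day 29 has none after any dose. One who stops after the Day 29 visit and before Day 78 has none after continued 10-mg or any 15-mg dosing. The gap matters for stoppers without symptoms or events. Their number is unknown and lies within the planned ceiling of 8 of 38, which itself rests on the assumed 20% discontinuation rate.

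The primary glucagon analysis and the other pharmacodynamic results use patients who complete both clamps, so no result or conclusion changes. This is a low-cost improvement to patient safety, not a flaw in the trial's inference.

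**What to change.** 1. In the Follow-up / Early Termination table, add a row for safety laboratory tests with X at ET, referring to Appendix 2: fasting where feasible, with fasting status recorded. Insert safety laboratory tests between vital signs and PK in that table's sampling order.
2. In Appendix 5, change safety-lab samples from 6 to up to 7 (7 × 15 = 105 mL) and the table total from 594 to 609 mL. Adjust the rounded 600 mL line to match, and note that completers have no ET draw.
3. In SAP 6.10.8, list all ET laboratory values, not only those out of range, under the treatment last taken. No summary time point is needed.

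The cost is one 15 mL tube at a visit that already draws PK and antibody samples, a fast where feasible, and some incidental values to follow up.
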